9.2. Causality

The relationship of each adverse event to the trial device may be determined by the manufacturer and/or a medically qualified Investigator according to the following definitions:

Not related: The event is clearly related to other factors such as the patients/participants clinical condition, therapeutic intervention, concomitant medication.

Unlikely: The event is probably produced by other factors such as the patients/participants clinical condition, therapeutic intervention, concomitant medication and does not follow a known response pattern to the device

Possibly: The event follows a reasonable temporal relationship from the time of placement/administration and/or follows a known response pattern to the device but could have been caused by other factors such as the patients/participants clinical condition, therapeutic intervention, concomitant medication.

Principal Investigator:

[name]

Short Title:

6-APP Study

Ethics Ref:

insert

Most probable: The event follows a reasonable temporal relationship from the time of placement/administration and/or follows a known response pattern to the device and could not have been caused by other factors such as the patients/participants clinical condition, therapeutic intervention, concomitant medication. Further the event immediately follows the administration/placement of the device and improves on stopping or removing the device.

9.3. Procedures for Recording Adverse Events

All adverse events (including ADEs) and device deficiencies occurring during the course of the study will be recorded on the CRF whether or not attributed to the trial device. The information recorded will include but not be limited to:

- A description of the event
- The dates of the onset and resolution
- Action taken
- Outcome
- Assessment of relatedness to the device
- Whether the AE is serious or not
- Whether the AE arises from device deficiency
- Whether the AE arises from user error

The severity of events will be assessed on the following scale: 1 = mild, 2 = moderate, 3 = severe.

AEs/ADEs considered related to the device as judged by a medically qualified investigator or the Sponsor will be followed either until resolution, or the event is considered stable.

It will be left to the Investigator's clinical judgment to decide whether or not an AE/ADE is of sufficient severity to require the participant's removal from treatment. A participant may also voluntarily withdraw from treatment due to what he or she perceives as an intolerable AE/ADE. If either of these occurs, the participant must undergo an end of trial assessment and be given appropriate care under medical supervision until symptoms cease, or the condition becomes stable.

9.4. Reporting Procedures for Serious Adverse Events

Reporting of all Serious Adverse Events will be done in accordance with the European Commission Guidelines on Medical Devices Serious Adverse Event Reporting (MEDDEV 2.7/3; December 2010).

SADEs/USADEs that pose an immediate risk to patient health or safety, will be reported to the OUH R&D team immediately or no later than 24 hours after the Investigator is aware. All information must be recorded on an SAE form and emailed to R&D at [contact].

R&D will perform an initial check of the report, request any additional information, and ensure it is reviewed by the Medical Monitor on a weekly basis. It will also be reviewed at the next Trial Safety Group meeting.

This information will also be reported to the device manufacturer, competent authority and the REC within 2 calendar days of the Chief Investigator becoming aware of the event.

Principal Investigator:

[name]

Short Title:

6-APP Study

Ethics Ref:

insert

SAEs/SADEs will be recorded for a 24 hour period following the use of the device. All SAEs will be followed up to resolution.

9.5. Safety Monitoring Committee

The Oxford University Hospitals Trust / University of Oxford Trials Safety Group (TSG) will conduct a review of all SAEs/SADEs for the trial reported during the quarter and cumulatively. The aims of this committee include:

- To pick up any trends, such as increases in un/expected events, and take appropriate action
- To seek additional advice or information from investigators where required
- To evaluate the risk of the trial continuing and take appropriate action where necessary

10. STATISTICS AND ANALYSIS

10.1. Description of Statistical Methods

Data will be analysed when the study is completed.

Statistical methods that will be employed to analyse and validate the results of the study are:

- Descriptive statistics (mean, standard deviation, median, interquartile range)
- Pearson correlation coefficients
- Distribution plots
- Scatter plots
- Bland Altman charts
- Error bars and confidence intervals

10.2. Number of Participants

This is an exploratory observational study and therefore no sample size calculation is provided, we propose collecting data on 30 participants.

10.3. Analysis of Outcome Measures

All participants' data will be used excluding those who withdrew consent.

Primary Objective:

Principal Investigator:	[name]	Ethics Ref:	insert
Short Title:	6-APP Study		

O1: We will measure the percentage of participants who perform at least one home 6MWT between baseline visit and 3-month visit and the percentage of participants who perform at least one home 6MWT between baseline visit and 6-month visit. These two percentages will be used as the main measure of the success of this study.

In addition, the distribution over time of when home performed tests will be computed.

Secondary Objectives

O2: We will compute the mean and standard deviation of the difference in distance as measured by the physiologists and the app. To evaluate the agreement between the two approaches, a Bland Altman graph will be also prepared.

O3: We will compute the correlation of the distance as computed by the app when used at home within 3 days from the hospital visit with the one gathered in the hospital 6MWT test.

O4: Ease of use, acceptance and mobile phone affinity will be measured with standard questionnaires. Compliance with the use of the app will be measured by counting the frequency of use of the app. Simple descriptive statistics will be computed and correlations among quantities will be explored. A selected number of participants will be chosen for semi-structured interviews in order to gain a deeper understanding of their usage of the app.

Tertiary Objectives

O5: Descriptive statistics about the walked distance, blood oxygen saturation and heart rate, BORG scale and number of steps will be used to compare changes before and after initiation of new therapies.

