4. OBJECTIVES AND OUTCOME MEASURES

Objectives	Outcome Measures	Timepoint(s) of evaluation of this outcome measure (if applicable)
Primary Objective O1: To demonstrate that patients are able and willing to use the app for the 6MWT	Percentage of participants who perform app-based home 6MWT	TP 1: 3 months after baseline visit TP 2: 6 months after baseline visit
Secondary Objectives O2: To validate app 6MWT measurements against the hospital 6MWT. O3: To compare the outdoor 6MWT app with the hospital based 6MWT.	Average and variability of the difference in distance as measured by physiologists and the app. Correlation of outdoor 6MWT app parameters with the hospital 6MWT test.	TP 1: at baseline visit TP 2: at 3-month visit TP 3: at 6-month visit TP 1: baseline visit 6MWT compared with following home test TP 2: 3-month visit 6MWT compared with closer home test before or after TP 3: 6-month visit 6MWT compared with closer home test before or after

Principal Investigator:

[name]

Short Title:

6-APP Study

Ethics Ref:

insert

O4: To assess the usability and acceptance of the app and the physicians' website.	Standard usability and acceptance questionnaire to users assessing their use of the app and website, semi structured interviews, analysis of technical logs.	TP 1: at 6 months after baseline visit
Tertiary Objectives	O5: To test whether the 6MWT app can detect changes in 6MWT distance more effectively than the hospital 6MWT, in patients starting advanced therapies.	Comparison of change in 6MWT app measurement with hospital 6MWT measurement, measured before and after initiation of new therapies.

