7. STUDY PROCEDURES

7.1. Recruitment

Principal Investigator:	[name]	Ethics Ref:	insert
Short Title:	6-APP Study		

Patients undergoing follow up in the PAH clinic will be eligible for participation. They will be approached by a member of the clinical team for consideration and recruited. We will recruit 30 compliant patients to enrol in the study.

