7.6. Discontinuation/Withdrawal of Participants from Study

Each participant has the right to withdraw from the study at any time. In addition, the Investigator may discontinue a participant from the study at any time if the Investigator considers it necessary for any reason including:

- Pregnancy
- Ineligibility (either arising during the study or retrospectively having been overlooked at screening)
- Significant protocol deviation
- Significant non-compliance with study requirements
- Withdrawal of Consent
- Loss to follow up

If participants withdraw from the study, their data until that point will still be analysed, unless deletion of data is requested by the participant (e.g., by withdrawing consent). Any participant that withdraws from the study will be replaced with a new participant. The reason for withdrawal will be recorded in the CRF.

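### The O1 percentages leave out participants who withdraw consent, and replacements fill their places, so the main measure of success is expected to be biased upward

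*Combined protocol and SAP*

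**What the plan says.** Section 4 gives the primary objective, O1, as "To demonstrate that patients are able and willing to use the app for the 6MWT". Section 10.3 has two measures of it. One is the "percentage of participants who perform at least one home 6MWT between baseline visit and 3-month visit"; the other is the same figure with the window extended to 6 months. On their role it says: "These two percentages will be used as the main measure of the success of this study". No numerical threshold is set.

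The sentence that opens Section 10.3, and so governs O1 as well as the other objectives, is: "All participants' data will be used excluding those who withdrew consent".

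Section 7.6 has two rules that bear on this. For participants who withdraw, "their data until that point will still be analysed, unless deletion of data is requested by the participant (e.g., by withdrawing consent"). And: "Any participant that withdraws from the study will be replaced with a new participant".

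Section 10.2 plans 30 participants without a sample size calculation. No section reports O1 on all enrolled participants, counts consent withdrawals as non-users, or plans a sensitivity analysis for them.

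**The concern.** For O1, the exclusion depends on something close to the outcome. Hospital walk tests are already part of routine outpatient reviews (Section 5). Much of what the study adds for the participant is use of the app, in hospital and then at home weekly or at least monthly (Sections 7.4 and 7.5). Someone who enters and later withdraws consent may well be showing the unwillingness that O1 is meant to detect. Under Section 10.3 that person disappears from the calculation, and under Section 7.6 a new recruit takes the place.

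At stake is the headline result. If those who withdraw consent are less likely to have done a home test, both percentages are too high. For a given difference in use, the error grows with the fraction who withdraw, so poor acceptance would be the hardest to see. Replacement brings the number back up, so the loss does not show in the denominator.

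**Working it through.** The plan has no calculation to reproduce: it gives no target rate, withdrawal rate, alpha or power. What follows is sensitivity arithmetic.

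**Inputs**
- Number analysed after replacement: 30 (Section 10.2).
- x = analysed participants with at least one home test; p = x/30 is the reported proportion. Assumed values: 24 (80%) and 27 (90%).
- w = participants who withdrew consent after baseline and were replaced. Not given; assumed.
- q = share of those w who did a home test before leaving. Not given; varied from 0 to 1.

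**Formulas**
- Plan's percentage: p = x/30.
- All-enrolled percentage: (x + qw)/(30 + w).
- Bias: p − (30p + qw)/(30 + w) = w(p − q)/(30 + w). This is the fraction who withdrew consent, times the difference in use between those analysed and those removed.

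**Varying w, with q = 0 and a reported 27/30 = 90.0%**

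| w | All enrolled | Bias (points) |
|---|---|---|
| 1 | 27/31 = 87.1% | +2.9 |
| 3 | 27/33 = 81.8% | +8.2 |
| 6 | 27/36 = 75.0% | +15.0 |

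The plan would report 90% in all three rows.

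**Varying q, with w = 3 and a reported 24/30 = 80.0%**

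| q | All enrolled | Bias (points) |
|---|---|---|
| 0 | 24/33 = 72.7% | +7.3 |
| 0.5 | 25.5/33 = 77.3% | +2.7 |
| 0.8 | 26.4/33 = 80.0% | 0 |
| 1 | 27/33 = 81.8% | −1.8 |

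**Direction.** The bias is upward when q is below p, zero when they are equal, and downward when withdrawers used the app more than those retained.

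**Which rule causes it.** If withdrawn participants stayed in the denominator and replacements were added to it, O1 would be computed on all 30 + w, and replacement would do no harm. The exclusion in Section 10.3 produces the bias; replacement restores n and hides the loss.

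**Scale.** The exact (Clopper-Pearson) 95% interval for 24/30 is 61.4% to 92.3%.

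**The case against.** The strongest reply concerns scope. Section 7.6 keeps the data of participants who leave, unless they ask for deletion, and lists consent withdrawal separately from loss to follow-up, non-compliance and protocol deviation. A reader might infer that the study recruits until it has 30 people who never dropped out. The text does not say so: leavers who neither withdraw consent nor ask for deletion keep their data, and if they are also replaced the total can exceed 30. Whether they count in the O1 denominator is not spelled out, but that is an ambiguity and not an exclusion. This part of the reply stands and limits the point to consent withdrawals.

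Size and direction are also open. O1 needs only one home test, and Section 7.4 asks for one within 3 days of baseline, so a later withdrawer may already have done one. Nor is app use the only added task: Sections 7.4 and 7.5 add exertion ratings, a usability questionnaire and, for some, an interview. Under Section 7.3 participants need give no reason for leaving. Upward bias is therefore expected but not certain, and the q = 0 figures are the upper end for a given w and p.

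A reader might also take the sentence "We will recruit 30 compliant patients to enrol in the study" in Section 7.1 as selection on the outcome. No compliance test, run-in or criterion in Sections 6.2, 6.3 or 7.2 gives that word any operation, so it carries no weight here.

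Finally, the study is exploratory and sets no threshold or test, so no formal decision can flip, and with few withdrawals the bias is smaller than the sampling uncertainty. That lowers the severity. It does not justify a success measure whose denominator drops people for a reason plausibly linked to the outcome. An interval around the reported figure does not correct for that either.

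**Conclusion.** The point holds for consent withdrawals. Sections 10.3 and 7.6 together remove these participants from both parts of the O1 percentages and fill their places, with no all-enrolled figure to set beside the result. The expected bias is upward, of size w(p − q)/(30 + w). With one consent withdrawal it is at most about 3 points at a reported 90%. With three and q = 0 it is 7.3 points at a reported 80% and 8.2 at 90%. It vanishes if withdrawers used the app as often as the rest, and reverses if they used it more.

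These sizes rest on assumed values of w and q, for which the documents give no figure. They do not support a claim that O1 is certainly inflated, or that every dropout is excluded. This should be fixed before analysis, but it does not invalidate the study.

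**What to change.** In Section 10.3, define the O1 denominator as every participant who consented and completed the baseline visit, including those who later withdraw consent and all other leavers. In Section 7.6, state that replacements add to this denominator and do not substitute for anyone in it.

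Count a participant as having performed a home test if one was recorded in the relevant window before leaving and the data may be kept; otherwise count not performed. Where deletion is requested, keep only the head count. Participants found ineligible in retrospect, or discontinued for pregnancy before any home test, may be listed separately, since neither shows unwillingness.

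Report the numbers withdrawn and replaced, and give the percentage as now planned as a sensitivity analysis with a confidence interval. The existing exclusion can stay for O2, O3 and O5.

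The cost is wording in two sections and a head count of enrolments and withdrawals, which needs neither retained app data nor a reason for leaving. The reported percentage may be slightly less favourable, and the rule is conservative for withdrawers whose deleted data included a home test.

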1. SYNOPSIS

Study Title	Evaluation of a new 6 minute walk test smartphone app in patients with pulmonary arterial hypertension (the 6-APP Study)	
Internal ref. no. / short title	6-APP Study	
Study Design	Comparison of standard 6 minute walk test with 6 minute walk test smartphone app	
Study Participants	Patients with, or being assessed for, pulmonary hypertension	
Planned Sample Size	30	
Planned Study Period	Q4 2017- Q4 2019	
	Objectives	Outcome Measures
Primary	To demonstrate that patients are able and willing to use the app for the 6MWT	Percentage of participants who perform app-based home 6MWT
Secondary	
To validate app 6MWT measurements against the hospital 6MWT
 
To compare the outdoor 6MWT app with the hospital based 6MWT
 
To assess the usability and acceptance of the app and the physicians' website
	
Average and standard deviation of the difference in distance as measured by physiologists and the app
 
Correlation of outdoor 6MWT app parameters with the hospital 6MWT test.
 
Standard usability and acceptance questionnaires, semi structured interviews, analysis of technical logs

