5. STUDY DESIGN

We propose to evaluate a novel approach to service delivery by monitoring PAH patients using an established m-health system to send 6MWT results to a central server where they can be accessed by the clinical team (Figure 1). The system includes a mobile phone “app” to allow participants to comfortably perform the 6MWT at home (indoors or outdoors). In the outdoor scenario, the app makes use of GPS to track the user’s position. In the indoor scenario it uses the phone’s accelerometer and magnetometer (compass) to count the number of laps over a fixed-length walkway.

[figure not shown]
Figure 1. Diagram of the system

Principal Investigator:
Short Title:

[name]
6-APP Study

Ethics Ref:

insert

Undertaking a 6MWT test within the participant's home environment, using mobile technology to transmit the results via a software application on a mobile phone is appealing as it is likely to be more acceptable to the participant, may provide more consistent and functionally relevant data, and may reduce hospital attendances and healthcare costs. By utilizing biometric collection devices such as a pulse oximeter monitor with Bluetooth capability, telehealth can be used to capture the oxygen saturation levels in the blood from participants and transmit them to a secure server, allowing them to be reviewed by cardiologists and other healthcare professionals.

This study aims to compare the indoor 6MWT, with the hospital performed 6MWT. It will assess the feasibility and acceptance of a mobile phone app as an instrument to measure the 6MWT.

The 6MWT is currently undertaken at every Outpatient appointment, normally at 0- 3-, 6- and 12-month outpatient reviews. The participant would perform a hospital based 6MWT, whilst simultaneously using the indoor version of the app on their own mobile phone at baseline, 3- and 6-month follow up. This will demonstrate to the participant how to use the app, and we will be able to understand whether they are able to use it correctly. It will also allow direct comparison of the standard 6MWT distance measurement with the measurement provided by the app.

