The participant will be then invited to use the app in their local environment, preferably in the outdoor scenario, and the collected information would then be transmitted to the hospital servers where it could be reviewed. The app could be used many times prior to attendance in outpatients, giving the clinicians more detailed information as to the overall functional status of the patient. Participants will be required to perform a test before and after their follow up appointments so that home-based measurements can be compared to hospital-based ones. They will be allowed to do as many tests as they are willing to, preferably once per week and at least each month.

Principal Investigator:

[name]

Short Title:

6-APP Study

Ethics Ref:

insert

In total, we aim to collect 3 indoor hospital-based measurements (baseline, 3- and 6-month) and at least 5 outdoor home measurements, one close to each hospital visit plus one between two visits. The data collected will allow us to understand the usage of the app by participants, validate the indoor measurements and correlate the home measurements with the hospital-based ones.

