7.4. Baseline Assessments

The baseline assessment will be a standard 6MWT which measures resting heart rate and oxygen level at rest, the distance walked over 6 minutes, then the oxygen saturations and heart rate at end of the 6MWT. Prior to the initiation of the test, participants will be asked to download the app onto their personal mobile phones. Participants will also be asked to use the app in its indoor mode, while performing the test in hospital. Participants who are not able to either download the app or use it correctly will be unable to participate. We will be using the BORG questionnaire at the end of both the app test and the hospital 6MWT. The Borg Rating of Perceived Exertion (RPE) is a way of measuring physical activity intensity level. Perceived exertion is how hard a patient feels they are working. It is based on the physical sensations a person experiences during physical activity, including increased heart rate increased breathing rate, increased sweating, and muscle fatigue. Although this is a subjective measure, a person's exertion rating may provide a fairly good estimate of the actual heart rate during physical activity (11). During activity, the patient uses the Borg Scale to assign numbers as to how hard they think they are working. Participants will be provided with the questionnaire at the end of their

Principal Investigator:

[name]

Short Title:

6-APP Study

Ethics Ref:

insert

6MWT and are encouraged to complete the questionnaire by the app or by the hospital physiologist. The physiologists undertaking the test will measure the distance walked using the system website to record the measurement. This way all measurements will be digitally available in one place. At the end of the assessment, participants will be asked to perform a home-based 6MWT within 3 days of the visit and 1 home test per week, or, at least, one per month.

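### O3 sets out to compare home outdoor walks with hospital walks, but its only assigned analysis is a correlation, which cannot show a systematic difference; its pairing wording also needs aligning

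*Combined protocol and SAP*

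**What the plan says.** Section 4 words the objective as "To compare the outdoor 6MWT app with the hospital based 6MWT". The outcome measure beside it, repeated in the synopsis, is "Correlation of outdoor 6MWT app parameters with the hospital 6MWT test". Section 10.3 gives the analysis: "We will compute the correlation of the distance as computed by the app when used at home within 3 days from the hospital visit", set against the hospital test.

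The mean and SD of the difference and the Bland-Altman graph are assigned in section 10.3 to O2, the comparison of app and physiologist. Section 5 describes the walks behind O2: the participant does the hospital test "whilst simultaneously using the indoor version of the app on their own mobile phone". Section 10.1 lists descriptive statistics, scatter plots, Bland-Altman charts and confidence intervals for the study in general, without tying any of them to an objective.

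On pairing, section 4 uses the next home test after baseline and, later, for example, "3-month visit 6MWT compared with closer home test before or after", with no time window. Section 10.3 sets a 3-day window, which fits the instruction in section 7.4 that participants are "asked to perform a home-based 6MWT within 3 days of the visit" and the reminder in section 7.5. On mode, O3 is framed as outdoor, but section 10.3 refers only to use at home. Section 5 allows home tests in either mode and asks participants to "use the app in their local environment, preferably in the outdoor scenario".

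**The concern.** A comparison of two ways of obtaining a walking distance should say how far apart they are. Correlation measures how closely the pairs follow a straight line, whatever its intercept and positive slope. Home distances that all read 42 m short, or 10% short, give the same r as home distances with no bias.

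This matters because evidence on outdoor mode is thin. Section 8.2 reports its accuracy from 24 lab tests (average error 11.23 m, maximum 27.19 m), whereas the 46 indoor-mode tests include actual patients. O3 is the only assigned analysis that sets patients' outdoor distances against their hospital distances at each visit. Clinicians are meant to review home results, and to read one beside a hospital result they need the size and direction of any offset in metres.

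The pairing wording adds a smaller problem. Sections 4 and 10.3 select different pairs when the nearest home test is more than 3 days from the visit, and section 10.3 has no rule for several tests inside the window. If indoor home tests enter the analysis, it no longer addresses the outdoor objective.

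**Working it through.** The plan gives no precision, power or target figure for O3, so there is none to reproduce.

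**Inputs from the documents.** 30 participants (section 10.2); three visits, hence at most 30 pairs per visit and 3 × 30 = 90 in all; 42 m as the improvement regarded as clinically significant (section 3).

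**Assumptions, not in the documents.** Between-patient SD of hospital distance, sd_b, 80 to 120 m; SD of the home-minus-hospital difference, sd_d, 30 m, with a range of 20 to 40 m and 60 m as a stress case; mean walk 400 m.

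**Step 1: what r responds to.** Write home = hospital + shift + d, with d independent of the hospital distance. Then r = sd_b / √(sd_b² + sd_d²). The shift does not appear.

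| sd_d | sd_b = 80 m | sd_b = 100 m | sd_b = 120 m |
|---|---|---|---|
| 20 m | 0.970 | 0.981 | 0.986 |
| 30 m | 0.936 | 0.958 | 0.970 |
| 40 m | 0.894 | 0.928 | 0.949 |
| 60 m | 0.800 | 0.857 | 0.894 |

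Each entry is the same for a shift of 0, 20 or 42 m. Sampling error does not help: for r = 0.958 and n = 30, the Fisher interval tanh(atanh 0.958 ± 1.96/√27) is 0.91 to 0.98 at every shift.

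**Step 2: numerical check.** In one illustrative set of 30 pairs, r was 0.947 with no bias. It stayed at 0.947 with shifts of +42, −42 and +100 m, and with all home distances multiplied by 1.2 or 0.8 (mean differences of about +79 and −79 m).

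**Step 3: what a paired difference would show.** The 95% CI half-width is t(n−1, 0.975) × sd_d / √n.

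| sd_d | n = 30 | n = 20 | n = 15 |
|---|---|---|---|
| 20 m | 7.5 m | 9.4 m | 11.1 m |
| 30 m | 11.2 m | 14.0 m | 16.6 m |
| 40 m | 14.9 m | 18.7 m | 22.2 m |
| 60 m | 22.4 m | 28.1 m | 33.2 m |

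Even the widest, 33.2 m, is below 42 m, so an observed mean difference of 42 m would have an interval excluding zero throughout.

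**Step 4: limits of agreement.** These are mean ± 1.96 × sd_d. With sd_d = 30 m they are −58.8 to +58.8 m for no shift and −100.8 to +16.8 m if home walks are 42 m shorter.

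**Step 5: constant or proportional bias.** Multiplying home distances by 0.9 gives a mean difference of −0.1 × 400 = −40 m. With sd_b = 100 m and sd_d = 30 m, the SD of the difference is √((0.1 × 100)² + (0.9 × 30)²) = √829 = 28.8 m, and the limits are −40 ± 56.4, or −96 to +16 m. That is close to the −42 m shift. The mean and limits therefore separate either bias from none, but not one kind from the other; for that, look for a trend in the Bland-Altman plot.

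**The case against.** The best defence is that correlation was a deliberate choice. Section 5 itself speaks of validating the indoor measurements and correlating the home ones. Agreement statistics go to O2, where both instruments measure the same walk. O3 pairs different walks, days apart and in different settings, and section 3 expects walks away from the clinic to reflect functional status better, so equality is not the hypothesis. The general methods list in section 10.1 would allow means and scatter plots that reveal a shift. The pairing texts can be read together as the closest test within 3 days, and section 5 plans outdoor home tests near each visit. The study is exploratory and judges its success on O1.

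Some of this stands. A home-hospital difference is not a failure of the app: it mixes GPS error with real differences in walking, and must not be reported as app error. The pairing texts are not strictly contradictory. The 20 to 40 m range for the difference SD may be too narrow; at 60 m, r falls to 0.80–0.89 for between-patient SDs of 80 to 120 m.

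It does not remove the mismatch. The stated objective is still a comparison, and a real difference between settings is also something r cannot show. A general list of methods does not commit the report to a paired difference for O3. The exploratory design explains why there is no sample-size calculation, not why the analysis leaves its objective unanswered.

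**Conclusion.** The point holds. As written, no analysis assigned to O3 estimates the difference between home outdoor and hospital distance in metres. That r ignores shifts and positive rescaling is algebra and rests on no assumption. The figures for r, CI width and limits depend on the assumed SDs. Across the ranges used, r is between 0.80 and 0.99 whatever the constant shift, while 15 to 30 pairs estimate the mean difference to within about ±7.5 to ±33 m. The pairing and mode wording is a matter of alignment rather than contradiction. The change should be made, but the weight is moderate: O3 is secondary and the primary objective is unaffected.

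**What to change.** - **Analysis (section 10.3).** For O3, add the mean paired difference, home outdoor minus hospital, with its 95% CI, a Bland-Altman plot and 95% limits of agreement. Do this per timepoint, or pooled by a method that allows for up to three pairs per participant. Keep the correlation as supportive.
- **Interpretation.** Show 42 m as context for the bias and limits, not as a pass/fail margin, since section 3 gives it as a threshold for improvement. State that the difference combines measurement error with real differences in walking.
- **Pairing (sections 4 and 10.3).** Use one rule: the closest outdoor-mode home test within 3 days of the visit, taken after the visit at baseline. Report indoor-mode home tests separately.
- **Conforming edits.** Update the O3 outcome line in the synopsis and section 4. State that the hospital value is the physiologist's distance. Settle whether O3 covers distance only (section 10.3) or other app parameters too (synopsis and section 4).

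The cost is some wording and a few lines of analysis on data already to be collected. The main downside is fewer pairs if some home tests are indoor or fall outside the window: at a difference SD of 30 m, the CI widens from about ±11 m with 30 pairs to ±17 m with 15.
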